#### 5.7.1.4 Multiple Comparisons/Multiplicity

There will be no adjustment for multiplicity.

#### 5.7.1.5 Planned Analyses

**Interim Analysis:** No interim analyses are planned.

#### 5.7.1.6 Examination of Subgroups

To evaluate the consistency of treatment effects, subgroup analyses will be explored for the primary and selected secondary efficacy endpoints based on:

- Age (18-65 or >65)
- Gender (Male, Female)
- Country (Austria, France, Germany, and Poland)
- Presence or absence of background of atopy (the stratification factor for randomization to the treatments)
- Baseline number of prurigo nodularis nodule (< median vs.  $\geq$  median), if exact counts are not available in the database then use (20-100 vs. >100) categories as classes.

Subgroup analyses will be explored for safety endpoints (e.g., AEs) based on:

- Age (18-65 or >65)
- Gender (Male, Female)

- Country (Austria, France, Germany, and Poland)
- Presence or absence of background of atopy (the stratification factor for randomization to the treatments)

If the number of subjects in a subgroup is too small, subgroups may be pooled for analyses.

Decisions regarding merging subgroups or eliminating some subgroups will be made at the blinded review before treatment unblinding and database lock.

Summary statistics will be provided for each of the subgroups by time points. The estimated mean change of treatment groups and 95% CI will be calculated and displayed graphically using forest plots for subgroup.

### 5.7.2 Primary Efficacy Endpoint

Pruritus Numeric Rating Score (NRS) is a scale to be used by the subjects to report the intensity of their pruritus (itch) during the last 24 hours all along the study from the first screening visit to the follow up visit.

The primary variable for the assessment of efficacy is the percent change from baseline in NRS at week 4 of average of the peak pruritus.

An analysis of variance (ANOVA) model will be used to test the difference between the nemolizumab and placebo treatments with percent change from baseline in NRS scores at week 4 being the dependent variable, and treatment, presence or absence of atopy and country terms as factors.

A 95% Confidence for the difference in LSmeans of treatments and p-value will be calculated based on contrast test statistics.

Other covariates may be explored and will be added into the model, if appropriate.

**Sensitivity analysis:** The robustness of the primary analysis will be investigated by performing the sensitivity analyses, as described in 5.7.1.3.

**Subgroup analysis:** The homogeneity of the treatment effect for a number of important subgroups will be investigated, as described in 5.7.1.6.

A by-subject listing of the primary efficacy data will be provided. In addition, a boxplot and line plots showing the mean percent change and 95% CI from baseline in NRS over time within each treatment group will be produced for ITT and PP populations.

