9.2 Statistical and analytical plans

A Statistical Analysis Plan (SAP) will be developed as a separate document. The SAP will contain detailed and technical description of specific data conventions, calculations and of statistical procedures for executing the analyses that are specified in the sections of the clinical trial protocol below.

Any changes made to analysis after finalization of SAP will be documented in the clinical study report.

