## 2 INTRODUCTION

This SAP describes the planned analysis and reporting for GALDERMA R&D, SNC, protocol RD.03.SPR.115828, entitled “A study to assess the safety and efficacy of nemolizumab (CD14152) in subjects with prurigo nodularis (PN)”, All Countries Amendment Version 2.0 dated Apr 09, 2018.

Prurigo nodularis (PN) is characterized by the presence of symmetrically distributed multiple (up to hundreds), highly pruritic, hyperkeratotic, erosive or crusted nodules and papules (Hyde JN et al., 1909). This leads to an impaired quality of life and high burden due not only to the severe itch but also the chronic, skin lesions and lack of treatment options (Warlich B., et al 2015).

The goal of PN treatment is to break the itch-scratch cycle and allow the skin to heal. Treatment of chronic pruritus is still notoriously challenging and frustrating for both dermatologists and patients as in the majority of cases, the response is either limited or associated with severe adverse events with the current therapy options. There is no standardized or approved therapy for PN up-to-date and evidence from controlled studies is limited (Fostini AC et al., 2013). The difficulty in treating this disease is reflected in the wide range of treatments proposed in the literature.

Nemolizumab (CD14152) is a humanized anti-human IL-31 receptor A (RA) monoclonal antibody that inhibits the binding of IL-31 to IL-31RA and subsequent signal transduction. IL-31 has been suggested to be a key player in the development of pruritus. Recent clinical studies of nemolizumab in patients with atopic dermatitis showed a rapid onset of pruritus reduction within one week followed by disease improvement (Ruzicka T et al 2017).

The main objective of this study is to evaluate the efficacy, safety and pharmacokinetics (PK) of multiple subcutaneous doses of nemolizumab in the treatment of pruritus and lesions associated to PN.

The planned analyses identified in this SAP may be included in the clinical study report (CSR), regulatory submissions, or future manuscripts. Also, post hoc exploratory analyses not necessarily identified in this SAP may be performed to further examine study data. Any post hoc, or unplanned, exploratory analyses performed, if included, will be clearly identified as such in the final CSR.

This SAP is based upon the following study documents:

- Study protocol, All Countries Amendment Version 2.0 (09 Apr 2018)

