**PD Analysis Population (PDAP):**

The PD statistical analyses will be performed based on the PP population, and after exclusion of samples unable to produce reliable quantifications of cytokines, and/or immunohistological markers and/ or transcriptomic biomarkers, due to the material quantity and/or quality.

The efficacy summaries and analyses will be based on the ITT population, which is based upon the Intention-to-Treat (ITT) principle. In the event that a subject is allocated the incorrect study treatment as per the study randomization list, subjects will be summarized and analyzed 'as randomized' (i.e., by randomized treatment group). In the event that a subject is stratified incorrectly, 'randomized stratum' will be used rather than 'actual stratum'.

For the primary and selected secondary efficacy endpoints, a sensitivity analysis will be performed on the PP population to assess the robustness of the study conclusions to the choice of analysis population. Subjects will be included in the analysis according to the treatment 'as randomized'.

The safety summaries and analyses will be based on the SAF population. Randomized subjects will only be excluded if there is clear, documented evidence that the subject did not receive any study drug injection. In the event that a subject is allocated the incorrect study treatment as per the study randomization list, subjects will be summarized and analyzed 'as treated' (i.e., by allocated treatment group).

Upon database release, protocol deviation and analysis population outputs will be produced and will be reviewed by Sponsor. An analysis population classification meeting will be arranged to discuss the outputs and to decide which subjects and/or subject data will be excluded from certain analyses. Decisions made regarding the exclusion of subjects and/or subject data from analyses will be made prior to database lock and unblinding and will be documented and approved by Sponsor.

The following analysis population summaries will be provided:

- The number and percentage of subjects in each study population will be presented by study treatment group including total (Analysis population: ITT).

A by-subject listing of analysis population details will be provided. This listing will be presented by treatment group and will include: subject identifier, inclusion/exclusion flag for each population and reason for exclusion from each population. All randomized subjects will appear on this listing.

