#### 5.7.1.3 Handling of Missing Data

**Use of rescue therapy:** For the purpose of efficacy analysis, subjects receiving any rescue therapies will be considered as treatment failures. All efficacy data, except Observed Case (OC), will be set to missing after rescue medication is used. In OC analysis, observed data after subject has received rescue treatment will be included.

**Diary data:** If a subject has less than 5 diary entries in a week, the weekly prorated average scores will be set to missing. Otherwise the method of computing weekly score when data are missing will be mean replacement approach. i.e. calculation of the overall weekly score a given week as 7 times average of non-missing average of that week.

The following methods will be used to impute the missing values:

**Continuous endpoints:** To impute the missing values for the primary and secondary endpoints, the following imputation approaches will be carried out to assess the robustness of study conclusions with choice of imputation method.

For sensitivity analyses, continuous endpoints will be analysed using analysis of covariance (ANCOVA) including terms of treatment group, country, presence or absence of background of atopy (the stratification factor for randomization to the treatments) and the corresponding baseline value.

1. **Last Observation Carried Forward (LOCF):** The primary imputation method for any missing data will be the LOCF approach. The last observed post-baseline value will be used to replace missing values for continuous variables. For questionnaire-based variables, LOCF will be applied to missing individual questions first, and the value of the total (or sub-scale) score will be derived based on the imputed individual questions.
2. **Observed Case (OC):** No data will be imputed. The observed values are used in analysis, including assessments post rescue medication.
3. **Multiple imputation (MI) method under assumption missing at random (MAR):**

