Multiple Imputation (MI) using the Missing At Random (MAR) assumption will also be used. The MI procedure of the SAS system will be used to generate five sets of data with missing values imputed from observed data. It is expected that the pattern of missing data will be monotonic, with slight deviations being corrected by the Markov Chain Monte Carlo (MCMC) method of the MI procedure. Linear regression will be employed to model the missing NRS score, with the following covariates included in the imputation model: treatment and non-missing data from earlier timepoints.

- **Analysis phase:** The imputed datasets will be analyzed using the methodology described for percent change from baseline in NRS score.
- **Pooling phase:** The results from the analysis of the multiple imputed datasets will be combined by the MIANALYZE procedure of the SAS system.

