## 5.11 Changes in the Conduct of the Study or Planned Analysis

Changes in the conduct of the study may be instituted through a protocol amendment. Planned analyses will be revised as appropriate. Similarly, planned analyses may be changed as a result of planned blinded data reviews. Changes will be finalized prior to database lock.

The ridit score is calculated combining data in the atopy and country stratum due to small sample size in each strata. The Placebo group is used as the reference group to calculate mean ridit score of the nemolizumab group using the method described in Uwawunkonye et. al. paper.

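### Does the SAP's remark about adding other covariates leave the primary model open?

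*SAP*

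**What the plan says.** SAP 5.7.2 defines the primary test as an ANOVA of percent change in peak NRS at week 4, with treatment, atopy and country. It then says: "Other covariates may be explored and will be added into the model, if appropriate".

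Other places bear on this sentence:

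- SAP 5.7.1.2 lists the covariates for the primary and secondary efficacy analyses: atopy and country. The additional covariates it allows are baseline NRS for absolute NRS change, and baseline DLQI for DLQI.
- SAP 5.5.1 and protocol 9.2.4 name the same two cofactors.
- SAP 5.11 allows planned analyses to change after planned blinded data reviews, and then: "Changes will be finalized prior to database lock".
- SAP 5.7.1.6, on subgroups: "Decisions regarding merging subgroups or eliminating some subgroups will be made at the blinded review before treatment unblinding and database lock". SAP 5.4, on populations: "Decisions made regarding the exclusion of subjects and/or subject data from analyses will be made prior to database lock and unblinding".
- SAP 2: "Any post hoc, or unplanned, exploratory analyses performed, if included, will be clearly identified as such in the final CSR". Protocol 9.2: "Any changes made to analysis after finalization of SAP will be documented in the clinical study report".

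On multiple imputation (MI), SAP 5.7.1.3 first says: "For sensitivity analyses, continuous endpoints will be analysed using analysis of covariance (ANCOVA) including terms of treatment group", together with country, atopy and the baseline value. Its MI paragraph then says: "The imputed datasets will be analyzed using the methodology described for percent change from baseline in NRS score". That method is the 5.7.2 ANOVA, which has no baseline term.

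**The concern.** A primary model should be fixed before anyone can see which version of it favours the drug. Read alone, the 5.7.2 sentence lets unnamed covariates into the model of the primary test. Its only condition is a judgement of appropriateness, and it does not say that the judgement is made blinded. The SAP does say so for subgroup merging and population exclusions, so the silence here is noticeable. Because 5.7.2 itself permits the addition, it could also be argued that an added covariate is neither a change to the plan nor a post hoc analysis, so that the safeguards in SAP 5.11, SAP 2 and protocol 9.2 would not apply. What is at stake is the 5% two-sided error of the single primary test.

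The second worry is that a programmer finds two models for the MI analysis of the primary endpoint. If MI used the baseline-adjusted model, a gap between it and the primary result would mix the effect of imputation with the effect of the extra term.

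**Working it through.** **The plan's own figure.** With difference 30, SD 35, two-sided alpha 0.05 and 90% power (protocol 9.3), the normal approximation gives n = 2 × (1.960 + 1.282)² × (35/30)² = 28.6, so 29 per group. The exact t test needs 30 (power 0.904; 29 gives 0.894). The stated 30 reproduces. At 35 per group the power is 0.942. The covariate sentence affects neither number.

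**Type I error by selection rule.** Inputs from the documents: 35 per arm, and a base model with treatment, atopy and country (four or five countries, since the SAP's lists differ). Assumed, because no document gives them: five independent normal candidates with joint R² with the outcome of 0 to 0.5. There is no treatment effect. Results for five candidates:

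| How the covariates are chosen | R² 0 | R² 0.10 | R² 0.3 | R² 0.5 |
|---|---|---|---|---|
| Blinded: lowest AIC without the treatment term | 4.83% | 4.85% | not run | 5.12% |
| Unblinded: those imbalanced at p < 0.1 | 5.3% | 4.4% | 3.9% | 3.3% |
| Unblinded: lowest AIC with treatment in the model | 5.9% | 5.9% | 5.8% | 5.1% |
| Most favourable of all 2⁵ = 32 models (four / five countries) | 7.58% / 7.95% | 9.62% / 9.84% | 14.08% / 14.41% | 18.58% / 18.90% |

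The fixed model gave 4.8% to 5.3% in the runs for the last row. Runs per cell were 8,000, 3,000, 3,000 and 10,000, top to bottom. The 3,000-run rows have a simulation standard error of about 0.4 points.

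With one candidate, picking the better of two models gave 5.72% at R² 0 (5.19% for the fixed model in the same runs, a rise of 0.5 points). At R² 0.10 it gave 6.47%, against 5.06%. A separate simulation of the most-favourable rule with five candidates and five countries gave 8.3%, 10.1% and 14.1% at R² 0, 0.10 and 0.3, in line with the last row.

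So knowledge of the allocation is not enough for serious inflation. The two unblinded but rule-based choices stay between 3.3% and 5.9%. The large figures require choosing the model for its treatment p-value.

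**Which MI model.** The ANCOVA sentence in SAP 5.7.1.3 is general and covers continuous endpoints in sensitivity analyses. The MI sentence is specific to the imputed datasets, and protocol 9.2.4 carries the same instruction with no competing ANCOVA sentence. The specific instruction governs, so MI uses the percent-change ANOVA. For observed cases (OC) only one model is given, the ANCOVA. LOCF is listed under that same sentence, so LOCF and OC can be compared on one model.

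**If a programmer chose the other MI model.** Inputs: difference 30, SD 35, 14.3% missing (5 of 35, the protocol's allowance), five imputations, and an assumed correlation r of baseline NRS with percent change.

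| r | SD of shift in treatment difference | Trials where significance differs |
|---|---|---|
| 0 | 1.13 points | 1.5% |
| 0.1 | 1.46 points | 1.9% |
| 0.2 | 2.15 points | 2.9% |
| 0.3 | 2.81 points | 4.2% |

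The standard error of the difference is about 9.1 points; with 30 observed per arm and no adjustment it is 35 × √(2/30) = 9.04. For OC the corresponding shift SD is 1.28 to 3.09 points.

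**The case for a change.** The strongest case for a change is that 5.7.2 reopens what 5.7.1.2 closes, and does so in the section that defines the primary test. SAP 5.11 never mentions covariates. SAP 5.5.1 lists more than five baseline characteristics, so five candidates is realistic. The secondary analyses of NRS, VRS and sleep NRS borrow the primary model, so the looseness could spread. Deleting one sentence would cost almost nothing.

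Part of this stands. The sentence fits poorly with the closed list, no operational criterion is given, and SAP 5.11 does not expressly govern it. The rest is a question of missing detail. The sentence is conditional at both ends, and two further SAP sections and the protocol fix the model. A statistician who reported a different model as primary would have to explain the departure from all of them. The SAP's stated route for altering an analysis is blinded review before lock, and SAP 5.7.1.5 plans no interim analysis that would unblind the data earlier. The supplied protocol does leave an interim look optional, with the study statistician unblinded (6.6.2 and 9.4). The SAP rests on protocol amendment 2.0, which is not among the documents.

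On MI, keeping a baseline-adjusted model for OC is a legitimate pre-specified sensitivity analysis. Preferring another model there is a matter of taste.

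**Conclusion.** No change to the plan is needed. The 5.7.2 sentence is loose drafting beside a primary model that SAP 5.7.1.2, SAP 5.5.1 and protocol 9.2.4 all fix as treatment, atopy and country. The sensible reading is that models with further covariates are exploratory, or are settled at the blinded review. Under blinded selection the simulated type I error is 4.8% to 5.2%. The 14% to 19% figures need two things that the documents do not support: five candidates explaining 30% to 50% of the variance, and a report of the best p-value among 32 models. They illustrate misuse and do not predict what this trial would do. The MI ambiguity resolves in favour of the specific instruction. At worst it moves a sensitivity estimate by an SD of 1.1 to 2.8 points, for assumed r of 0 to 0.3, against a planned difference of 30. These conclusions assume that amendment 2.0 keeps the ANOVA of the supplied protocol and that model decisions follow the blinded route in SAP 5.11.

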### 5.7.3 Secondary Efficacy Endpoints

#### 5.7.3.1 Assessment of pruritus and diary data by the Subject

##### Pruritus Numeric Rating Scale (NRS)

Absolute and percent change from baseline (Day 1) in weekly average of the peak and average pruritus NRS at each visit (Weeks: 1, 2, 4, 8, 12, 16, 18, E/T or unscheduled visit, if applicable) up to week 18.

The descriptive statistics for each time point and absolute change and percent change from baseline will be presented by each treatment group. Least square means, difference from baseline and 95% CI for that will also be provided at each assessment time point.

The percent and absolute change from baseline of peak and average NRS will be analyzed separately at each assessment timepoint using the ANOVA model described for the primary analysis above. For absolute change endpoint, the ANCOVA model, with the same factors as in the percent change model, will be performed, but with baseline NRS as a covariate.

A 95% CI for the treatment difference will be calculated for both absolute change and percent change of NRS from baseline and will be plotted by treatment group for ITT population.

**Sensitivity analysis:** Sensitivity analyses will be performed as described in 5.7.1.3.

**Subgroup analysis:** Subgroup analyses will be investigated as described in 5.7.1.6.

##### Verbal rating scale (VRS)

The VRS consists of a list of adjectives describing different levels of symptom intensity to be used by the subjects to report the intensity of their pruritus (itch) over the last 24 hours.

The intensity of subject's pruritus (itch) will be measured daily using the five-point scale, where 0 = no itch, 1 = mild itch, 2 = moderate itch, 3 = severe itch, 4 = very severe itch.

The efficacy endpoint for the VRS will be the absolute and percent change from baseline in weekly average of the peak and average VRS to each visit (Day 1, baseline, Week 1, 2, 4, 8, 12, 16, 18, E/T or unscheduled visit, if applicable). These endpoints will be compared with nemolizumab and placebo treatments using ANOVA model for the primary analysis described above separately at each assessment visit. For absolute change endpoint the ANOVA model will be performed, but with baseline VRS as an additional covariate.

A 95% CI for the treatment difference will be calculated for both absolute change and percent change of VRS from baseline and will be plotted by treatment group for ITT population.

### **Dynamic Pruritus Score (DPS)**

The 9-point DPS is a dynamic scale to be used by subjects to evaluate the change of their pruritus compared with an earlier time point (i.e. before injection on Day 1).

The details of measuring scale and assessment time are given in section 4.2.1.3. The data will be analyzed using a Cochran-Mantel-Haenszel (CMH) test with ridit scores between nemolizumab and placebo, stratified by by background of atopy (presence or absence) and country.

#### **5.7.3.2 Assessment of Prurigo by Physician**

##### **Investigator Global Assessment (IGA) of Prurigo**

IGA is a 5-point scale ranging from 0 (clear) to 4 (severe) used by the investigator or trained designee to evaluate the severity of the disease. The details of measuring scale and assessment time are given in section 4.2.1.4.

IGA evaluation of the severity of at each post-treatment timepoint will be summarized as a continuous variable and as a categorical variable, given its ordinal nature by treatment group. The data will be analyzed using a Cochran-Mantel-Haenszel (CMH) test with ridit scores between nemolizumab and placebo, stratified by by background of atopy (presence or absence) and country.

The shift table will also be provided for overall investigator-rated evaluation change from baseline to Week 18 for each treatment group and overall.

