9.2.4 Inferential statistical analyses

The primary efficacy analysis of the percent change from baseline to week 4 of the weekly average of the peaks pruritus NRS, will be an ANOVA including the Treatment group as factor, presence and absence of background of atopy and country as a cofactors.

In addition to the per-protocol analysis, several sensitivity analyses on ITT population will be conducted for the primary endpoint. For ITT, NRS will be set to missing after rescue medication is used.

- The primary imputation method for any missing data will be the LOCF (Last observation carried forward) approach.
- Multiple Imputation (MI) using the Missing At Random (MAR) assumption will also be used. The MI procedure of the SAS system will be used to generate five sets of data with missing values imputed from observed data. It is expected that the pattern of missing data will be monotonic, with slight deviations being corrected by the Markov Chain Monte Carlo (MCMC) method of the MI procedure. Linear regression will be employed to model the missing NRS score, with the following covariates included in the imputation model: treatment and non-missing data from earlier timepoints. The imputed datasets will be analyzed using the methodology described for percent change from baseline in NRS score. The results from the analysis of the multiple imputed datasets will be combined by the MIANALYZE procedure of the SAS system. The seed number to be used will be the protocol number (115828).

For secondary endpoints:

The percent change from baseline to any visits of the weekly average of the peak and of the average pruritus NRS, will be analyzed separately via an ANOVA including the Treatment group as factor, presence and absence of background of atopy and country as a cofactors. The absolute change will be analyzed via an ANCOVA, same factors as the percent change but with including baseline NRS as a covariate.

IGA, DPS and PAS will be analyzed at any visits by the CMH test stratified by background of atopy and by country with the ridit transformation and the row mean difference statistic (FREQ procedure from SAS).

Proportion of subjects achieving success (IGA=0[clear] or IGA=1[Almost clear] with two point improvement from baseline) will be analyzed at each evaluation visit using the Cochran-Mantel-Haenszel (CMH) test stratified by background of atopy and by country with the ridit transformation and the general association statistic (FREQ procedure from SAS).

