#### 4.2.1.4 Investigator Global Assessment of Prurigo (IGA)

IGA is a 5-point scale ranging from 0 (clear) to 4 (severe) used by the investigator or trained designee to evaluate the severity of the disease. IGA corresponds to the overall assessment of the severity of prurigo including presence of crust and nodules or skin bleeding that will be evaluated at Baseline, Week 4, Week 8, Week 12, Week 18 & in case of Early termination visit / Unscheduled visit, if applicable.

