### 5.2 General Presentation Considerations

Unless otherwise stated, descriptive summaries will be presented by treatment group. In all tables the treatment groups will be presented in the order of Placebo, Nemolizumab.

Continuous data will be summarized in terms of the mean, standard deviation (SD), median, minimum, maximum, lower quartile (Q1), upper quartile (Q3), and number of observations, unless otherwise stated. Where data are collected over time, both the observed data, change from

baseline and percent change from baseline when appropriate will be summarized at each time point. The minimum and maximum will be reported to the same number of decimal places as the raw data recorded in the database. The mean, median, Q1, and Q3 will be reported to one more decimal place than the raw data recorded in the database. The SD will be reported to 2 more decimal places than the raw data recorded in the database. In general, the maximum number of decimal places reported shall be four for any summary statistic.

Categorical data will be summarized in terms of the number of subjects providing data at the relevant time point (n), frequency counts and percentages. Percentages will be presented to one decimal place. A percentage of 100% will be reported as 100%. Percentages will not be presented for zero counts. Percentages will be calculated using n as the denominator. If sample sizes are small, the data displays will show the percentages, but any textual report will describe frequencies only. Changes from baseline in categorical data will be summarized using shift tables where appropriate.

P-values greater than or equal to 0.001, in general, will be presented to three decimal places. However, if a p-value is only presented to four decimal places (by SAS) it will not be rounded again, but will be presented to four decimal places. P-values less than 0.001 will be presented as “<0.001”, and p-values greater than 0.999 will be presented as “>0.999”.

Confidence intervals (CIs) will be presented to one more decimal place than the raw data.

All report outputs will be produced using SAS® version 9.3 or a later version in a secure and validated environment. The outputs will be provided as individual TLFs in RTF as well as PDF formats and all TLFs in one PDF bundle.

All statistical tests will be two-sided and will be performed at the 5% level of significance, unless otherwise stated.

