#### **Assessment of Prurigo Activity Score (PAS)**

The evaluation of the disease will be performed by the Investigator using the Prurigo Assessment Scale (PAS) at baseline and Week 12 using the entire scale and at week 4, 8,18 and in case of Early termination visit / Unscheduled visit, if applicable, using item 5 (number of lesions only) and 6 (excoriation/crusts and healed lesions).

PAS evaluation of the severity of at each post-treatment timepoint will be summarized as a continuous variable and as a categorical variable, given its ordinal nature by treatment group. The data will be analyzed using a Cochran-Mantel-Haenszel (CMH) test with ridit scores between nemolizumab and placebo, stratified by background of atopy (presence or absence) and country. The shift table will also be provided for overall investigator-rated evaluation change from baseline to Week 18 for each treatment group and overall.

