## 5.10 Determination of Sample Size

For the current study, it is assumed that the common standard deviation is 35 and that the true difference between Nemolizumab and the placebo is 30% in terms of percent change from baseline in worst itching score on a NRS at Week 4.

With an effect size of  $(30/35=) 0.857$ , a power of 90% and a type I error of 5% two-sided; at least 30 subjects are needed per group. In order to maintain the power of the tests, for per-protocol population, in case of drop outs/major deviations at Week 4, the sample size will be increased to 35 subjects per group, i.e. 70 to be randomized.

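### The IGA and PAS item 6 tests leave out the baseline category recorded before the first injection, which costs precision and protection against chance imbalance

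*SAP*

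**What the plan says.** SAP 4.2.2.2 defines the endpoints as the IGA category and the PAS item 6 stage at each visit, not as changes. SAP 5.7.3.2 tests IGA with a "Cochran-Mantel-Haenszel (CMH) test with ridit scores between nemolizumab and placebo, stratified by by background of atopy (presence or absence) and country". The PAS text names the same test ("CMH) test with ridit scores between nemolizumab and placebo, stratified by background of atopy (presence or absence) and country") without saying whether it covers item 5, item 6 or both. Protocol 9.2.4 agrees: "IGA, DPS and PAS will be analyzed at any visits by the CMH test stratified by background of atopy and by country".

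Baseline is available. IGA is "evaluated at Baseline, Week 4, Week 8, Week 12, Week 18" (SAP 4.2.1.4), PAS is scored in full at baseline (SAP 4.2.1.5), and protocol 8.1.2.1 places both before the first injection.

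Apart from baseline summaries (SAP 5.5.1), baseline is used as follows:
- **IGA category and PAS item 6 stage:** only a descriptive shift table to Week 18. SAP 5.7.1.2 lists no baseline covariate for them, and the sensitivity ANCOVA in SAP 5.7.1.3 is for continuous endpoints.
- **IGA success and PAS item 5:** baseline is in the definition (a two-point improvement; change in lesion number).
- **Absolute NRS change, absolute VRS change and DLQI change:** the baseline value is a covariate (SAP 5.7.1.2, 5.7.3.1, 5.7.4).

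**The concern.** Efficacy on prurigo lesions is a secondary objective, and IGA and PAS item 6 are two of its measures. Entry requires at least 20 nodules and an NRS of at least 7 (protocol 5.3) but sets no IGA grade or PAS stage, so starting severity can differ between subjects. Protocol 6.1.3 stratifies randomization by atopy only, so starting severity can also differ between arms.

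If starting severity predicts later severity, leaving it out has two effects. Variation that baseline could explain stays in the error and lowers power. An arm that happens to start worse also tends to end worse, and the test cannot separate that from a treatment effect. The plan guards against this for the itch and quality-of-life change scores, but not for these two ordinal lesion measures, and gives no reason.

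**Working it through.** **1. The plan's own figure.** SAP 5.10 assumes "the common standard deviation is 35 and that the true difference between Nemolizumab and the placebo is 30" percentage points on the primary endpoint, with "a power of 90% and a type I error of 5% two-sided".
- Normal approximation: n = 2(1.960 + 1.282)² / (30/35)² = 28.6, so 29 per group.
- Noncentral t: power is 0.894 at 29 and 0.904 at 30 per group.

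The stated 30 is reproduced. Then "the sample size will be increased to 35 subjects per group, i.e. 70 to be randomized". No power is stated for IGA or PAS.

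**2. Analytic size of the loss.** Adjusting for a baseline with correlation ρ to the outcome multiplies the residual SD by √(1 − ρ²). For a test with 80% unadjusted power at the two-sided 5% level of SAP 5.2:

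adjusted power = Φ(2.802/√(1 − ρ²) − 1.960); equivalent total N = 70(1 − ρ²)

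| ρ (assumed) | Power | Subjects giving the power of 70 |
|---|---|---|
| 0 | 80.0% | 70 |
| 0.2 | 81.6% | 67 |
| 0.3 | 83.6% | 64 |
| 0.5 | 89.9% | 53 |
| 0.7 | 97.5% | 36 |

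**3. How often the arms differ at baseline.** Exact binomial, 35 per arm. A difference of 10 percentage points or more means at least 4 subjects (3.5/35 = 10%); 20 points or more means at least 7.
- Half of subjects severe (assumed): 40% of trials and 12% of trials.
- 30% severe (assumed): 36% and 9%.

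**4. Simulation of the planned test.** From the documents: 70 subjects 1:1, a five-category outcome, the CMH mean-score test with ridits pooled over strata (SAP 5.11), and 2 atopy × 4 country strata (countries as in SAP 5.7.1.6), averaging 70/8 = 8.75 subjects. Assumed: latent shift 0.7 SD; baseline split 15/45/40% (mild/moderate/severe) or 50/50%; placebo outcome cumulative 2/10/35/70%.

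Common-slope rank ANCOVA: regress the pooled outcome ridit on the pooled baseline ridit with stratum effects and one slope, then apply the same stratified CMH statistic to the residuals.

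| Observed correlation (latent ρ) | Planned test | Common slope |
|---|---|---|
| 0 (0) | about 73% | about 72% |
| 0.22-0.25 (0.3) | 73-75% | about 75% |
| 0.38-0.42 (0.5) | 73-75% | 80-82% |
| 0.54-0.60 (0.7) | 73-75% | 87-89% |

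A separate run with slightly different baseline cuts gave 74-75%, 79-80% and 85-88% in the last three rows. Overall type I error was about 5% for both tests.

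**5. Two adjustments that go wrong here.**
- *A separate slope in each stratum*, with strata of about 9: at correlation 0.25 and a 15/45/40% baseline, power fell from 73.8% to 70.2%; at 0.42 it gained only about 2.5 points. With a 50/50 baseline it fell from 74.1% to 69.8% at 0.22.
- *Baseline as a further CMH stratum*: 16 to 24 strata of 3 to 4 subjects. At latent ρ 0.3 power was 66-69%, below the planned test.

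**6. Error conditional on an imbalance.** About 19% of simulated trials had a gap of at least 15 points in the worst baseline category. In those, the planned test rejected a true null in 6-7%, 9% and 11-13% at latent ρ of 0.3, 0.5 and 0.7, against 4-6% after adjustment.

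**The case against.** The planned test is a standard, pre-specified randomization-based test, and protocol and SAP agree on it. A reader might infer that omitting baseline makes it invalid. It does not: the overall error rate is about 5%, and the rates in step 6 apply only given an observed imbalance. A reader might also infer that the lesion objective ignores baseline. It does not: IGA success and PAS item 5 change both use it, and baseline IGA and PAS are summarized, so an imbalance would be visible.

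The size of the gain is not known. The target population is moderate to severe (protocol 3.2), so baseline may sit in one or two categories. On the healed-lesion row of PAS item 6, stage 4 covers 0-24% healed, and subjects with active disease may cluster there. The gain is then small. PAS item 6 was not simulated separately. The strata are already sparse, which SAP 5.11 acknowledges, so a careless adjustment can do harm.

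All of this stands as a limit on size and on the choice of method. It does not explain why these two tests alone should forgo a covariate already collected. The IGA success and lesion-count endpoints are different measures and do not repair the IGA and item 6 comparisons.

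**Conclusion.** The point holds as a matter of precision and of protection against chance imbalance, not of validity. Under the stated assumptions the gain is negligible near zero correlation, about 1 to 2 points at 0.22-0.25, roughly 5 to 8 points at 0.38-0.42 and 12 to 15 points at 0.54-0.60. These figures rest on an assumed effect, correlation and baseline distribution, none of which the documents give for IGA or PAS, and on four countries. With the five countries of the protocol synopsis, the strata would average 70/10 = 7 subjects.

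Both are secondary endpoints with no multiplicity adjustment (SAP 5.7.1.4). Nothing here touches the primary NRS conclusion, and the documents do not support a claim that it does.

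**What to change.** In SAP 5.7.3.2, for IGA and PAS item 6:
- Regress the pooled ridit of the post-treatment category on the pooled ridit of the baseline category, with stratum effects and one common slope. Apply the stratified CMH mean-score test already planned to the residuals.
- As an alternative, fit a proportional-odds model with treatment, baseline category, atopy and country.
- State that slopes are not fitted separately within strata and that baseline is not added as a CMH stratum.
- Keep the unadjusted CMH test as supportive.
- Say which PAS items the PAS test covers.

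The change needs a wording edit and a few lines of SAS, and no new data. SAP 5.11 allows changes finalized before database lock; protocol 9.2.4 names the unadjusted test, so the departure should be recorded. The downside is one extra analysis step and, at zero correlation, about one point of power (73.1% to 72.3% and 72.7% to 71.7% in the two simulated settings).
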